1.3 Criteria for stopping the study

All SAEs will be communicated to the DSMB. Depending on the nature of the SAE and its potential relationship to the study medication, the DSMB may request unblinding of the treatment allocation for any patient that suffers SAE(s) and will decide on further action.

17. Quality Assurance (QA)

17.1 Quality assurance monitor

A Contract Research Organization (CRO) will monitor this protocol.

17.2 Quality assurance plan

On-site monitoring will be carried out by the CRO. An initial visit will be conducted by the CRO, following final approval of the protocol by the IRB and FDA. During the initial visit, the study team and the monitor determined the frequency of monitoring visits. The frequency was set at yearly. The sponsor via the CRO, will be responsible for providing adequate oversight of the investigation to ensure adequate protection of the rights, welfare, and safety of human subjects and the quality and integrity of the resulting data.

18. ADVERSE EVENTS REPORTING

The Principal Investigator is responsible for detecting, documenting, and reporting unanticipated problems, adverse events (AEs), including serious adverse events (SAEs), and deviations in accordance with NIH policy, IRB requirements, and federal regulations. Relatedness to the research of all serious adverse events will be determined by the PI in consultation with the CD.

Serious unanticipated problems, serious adverse events (including deaths) that are not unanticipated problems, and serious protocol deviations will be reported to the IRB and CD as soon as possible and in writing on the Problem Report Form not more than 7 days after the PI first learns of the event, unless immediate reporting is waived for specific serious adverse events as noted below. Not serious unanticipated problems and not serious deviations will be reported to the IRB and CD as soon as possible and in writing on the Problem Report Form not more than 14 days after the PI first learns of the event.

All adverse events, deviations, and unanticipated problems will be summarized and reported at the time of Continuing Review.

The following expected Serious Adverse Events will not be reported to the IRB immediately and within 7 days unless they occur at a rate or severity greater than expected:

Hospitalization for urinary tract and kidney infections

Hospitalization for falls resulting in injury

These SAE's will be summarized at the time of continuing review. Serious adverse events occurring at a greater severity or frequency than expected will be reported as Unanticipated Problems as delineated above. The expected severity and frequency will be based upon each patient's pre-randomization history (baseline).

The NINDS, holder of the investigator-IND, or her/his representative is responsible for submitting reportable SAEs to the FDA under its private IND application, in accordance with Federal and NIH requirements. The NINDS is also responsible for providing Santhera Pharmaceuticals (Switzerland) Ltd. with copies of all Serious Adverse Drug Reaction reports concurrently with their submission to the FDA, including copies of any warning letters or other information affecting the safety and/or well-being of human subjects in research conducted under this CTA.

Santhera Pharmaceuticals (Switzerland) Ltd. is responsible, in collaboration with United BioSource Corporation (UBC) Geneva, for the processing of reportable SAEs received from the NINDS or her/his representatives. Santhera is also responsible for the submission of those reportable SAEs to Health Authorities (other than the FDA), Ethics Committees and Investigators taking part in studies with the same active moiety, as required by regulations. Moreover, Santhera Pharmaceuticals (Switzerland) Ltd. will transmit to the NINDS all reports of Serious Adverse Drug Reaction occurring in Santhera-sponsored studies and associated with the same active moiety, as well as any other information altering the safety profile of the study drug.

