9.1.16 Monitoring of adverse events

The patient will be instructed to contact the investigator immediately should the patient manifest any sign or symptom perceived as serious during the period extending from performance of the first study procedure (e.g. drawing of a blood sample) up to and including 1 month after the last dose (telephone interview at month 25). After this period of time, the patient should report to the investigator only adverse events that are serious and perceived as possibly related to their participation in this study.

Additionally, the patient will be instructed to contact the investigator immediately if he/she believes that he/she has fathered/conceived a child. Testing would be performed to verify that the subject or subject's partner was pregnant. If the pregnancy test were positive, the patient would be instructed to immediately stop taking the study drug and his/her treatment assignment would be revealed to the investigators and the DSMB. The patient or partner would be counseled and followed closely during the pregnancy by the NIH research team and would implement any recommendations made by the DSMB.

Patients will be physically examined by the investigator approximately every 6 months for the study duration. Extensive laboratory monitoring of the following will occur every 6 months for the study duration: CBC with differential, Chemistry panel 20, and urinalysis and pregnancy test (for females with childbearing potential). Additionally, laboratory monitoring (CBC, chemistry panel with liver function tests) will be performed every 3 months after initiation of dosing of idebenone for the first year of treatment and every 6 months thereafter.

All adverse events occurring within 1 month following the last administration of the study medication must be recorded on the Adverse Event Form irrespective of severity and seriousness, and whether or not they are considered related to the study medication. Additionally, all serious adverse events (SAE) brought to the attention of the investigator during the period starting from the day of performance of the first study procedure to the telephone interview on month 25, must be recorded and reported to the FDA in accordance with federal regulations and NIH procedures. Any SAE reported by the patient after month 24, will be subjected to expedited reporting only if judged to be related to the study treatment by the Investigator.

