16. DATA AND SAFETY MONITORING

16.1 Monitoring plan for the study as a whole

This study will be monitored by a Data and Safety Monitoring Board (DSMB). [name] [name] is a board-certified neurologist with full clinical privileges. She will serve as the Independent Medical Monitor. [name] is independent of NIB and will be involved in crucial decision making regarding clinical issues that may arise during this trial. We are instituting an NIB independent medical monitor as a way to mitigate [name] conflict of interest (COI). [name], the PI on the study, is co-inventor on an NIH patent related to the use of idebenone and as such will receive patent royalty payments.

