22. CONFLICT OF INTEREST/TECHNOLOGY TRANSFER

NIH guidelines on conflict of interest have been distributed to all investigators.

[name] has identified a conflict of interest related to this study. She is one of the co-inventors on an NIH patent related to the use of idebenone as therapeutic agents in humans. This conflict of interest is properly disclosed in the protocol and in the consent form.

To resolve this conflict-of-interest, we have instituted following safeguards:

- [name] will not obtain informed consent and will not serve as the treating or evaluating physician on this protocol.

- [name], a senior NINDS neurologist who is not part of the NIB, will serve as the Independent Medical Monitor under this protocol.
- The independent DSMB will monitor the study.

No other investigators identified any additional conflicts of interest.

A clinical trial agreement (CTA#2009-0004) has been established with Santhera Pharmaceuticals through the NIH/NINDS office of technology transfer (OTT). This agreement specifies that Santhera will provide idebenone without restriction for the clinical study as outlined. All collected raw data will be the sole property of NINDS. Summary data will be made available to Santhera Inc. for regulatory purposes and for stock exchange purposes. Santhera Inc. can use these summary data for other purposes only after consultation with NINDS and only under confidentiality agreement.

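### The conflict-of-interest plan does not cover SAE relatedness: Protocol section 18 gives that judgment to the PI, who has a royalty interest in idebenone, and no role in it is stated for the Independent Medical Monitor

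*Protocol*

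**What the plan says.** - **Who decides.** Protocol section 18: "Relatedness to the research of all serious adverse events will be determined by the PI in consultation with the CD". The Independent Medical Monitor is not mentioned there, and CD is not defined in the text available.
- **The interest.** Section 16.1 states that "the PI on the study, is co-inventor on an NIH patent related to the use of idebenone" and "as such will receive patent royalty payments".
- **The safeguards.** Section 22 lists three. The conflicted investigator "will not obtain informed consent and will not serve as the treating or evaluating physician on this protocol". A senior neurologist "who is not part of the NIB, will serve as the Independent Medical Monitor under this protocol". An independent DSMB monitors the study. Section 7.6.11 adds that the PI will not be a clinical evaluator.
- **The monitor's purpose and remit.** Section 16.1 says "We are instituting an NIB independent medical monitor as a way to mitigate" the conflict, and that this person "will be involved in crucial decision making regarding clinical issues that may arise during this trial".
- **Other text on causality.** Section 9.2.20 has the investigator grade each adverse event's relation to study medication on five levels. Under section 9.1.16, an SAE that the patient reports after Month 24 "will be subjected to expedited reporting only if judged to be related to the study treatment by the Investigator".
- **DSMB.** Sections 16.2.4 and 16.2.5 send all SAEs to the DSMB within 7 days and have it review them within 15 days of receipt. The section on stopping the study lets it request unblinding and decide what to do, in light of the event's nature and its possible link to study medication.

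**The concern.** The protocol recognises that a person with a financial stake in idebenone should not evaluate patients in a trial of it. It then gives that person the determining voice on whether each serious event is related, which is among the judgments closest to that stake.

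Long-term safety is the first primary goal. SAP section 14.2 evaluates treatment-emergent adverse events by relationship to study treatment, and the DSMB's response to an SAE depends partly on its possible link to the drug. If the recorded relationship leans one way, the safety description leans with it. Even without a lean, a reader of a favourable safety result could ask who made these calls, and the present text gives an awkward answer.

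**Working it through.** No arithmetic applies. The check sets the relevant provisions side by side.

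1. **Is the conflicted investigator the PI?** Yes. Section 16.1 identifies the PI as co-inventor and royalty recipient. Section 22 places its restrictions on the co-inventor and says that no other investigator declared a conflict.

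2. **Is relatedness an evaluative judgment?** Yes. Section 9.2.20 rests causality on the patient's clinical state, other treatments, and previous or published reactions. Its levels are soft: Probable and Possible differ in whether other factors can reasonably explain the event, so the identity of the assessor matters.

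3. **Does any listed safeguard cover it?**
   - The bar on taking consent, treating and evaluating does not mention SAE relatedness, and section 18 assigns relatedness to the PI.
   - The monitor's remit is general. Neither section 16.1 nor section 22 mentions SAE causality, and section 18 names only the PI and the CD.
   - The DSMB sees every SAE and can act, but nothing in the text available lets it or the monitor correct the relatedness that is recorded and later tabulated.

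4. **Does relatedness filter what oversight bodies see?** Largely no. The DSMB receives all SAEs. Section 18 sends SAEs to the IRB and CD within 7 days without regard to relatedness, apart from two expected types of hospitalisation. Section 9.1.16 requires SAEs known up to the Month 25 interview to be recorded and reported to the FDA. The one explicit filter is expedited reporting of SAEs that patients report after Month 24, and that section assigns the judgment to the Investigator, not to the PI by title.

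5. **Does blinding remove the risk?** It limits it. Sections 7.4 and 7.6.12 keep the code with the pharmacy until the database is locked, so a blinded assessor cannot knowingly downgrade events on idebenone only. A general lean towards unrelated would act on both arms and lower the absolute count of related events. However, section 7.6.11 accepts that some on-treatment data, immunological markers especially, may reflect allocation. It separates the other assessors for that reason and makes the PI the one person who sees all the data together.

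6. **Do the sections agree on the assessor?** Section 18 names the PI; sections 9.1.16 and 9.2.20 name the investigator. Section 18 concerns relatedness to the research, which can include procedures such as lumbar puncture or apheresis. The other two concern the study drug. They can be read together, but no rule says whose assessment is recorded if they differ.

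**The case against.** A reader might infer that the safeguards are bypassed, that the PI decides alone, or that the monitor was created for SAE causality and has been cut out. The documents support none of these. The DSMB is itself one of the three safeguards and sees every SAE unfiltered. The PI must consult the CD. The monitor's stated remit is general.

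A reader might also infer that the PI controls expedited reporting after Month 24, or that moving one or two events would change a comparison of related SAEs between arms. Section 9.1.16 gives the first judgment to the Investigator. As for the second, the primary safety endpoints in SAP section 4.1 are premature discontinuations, SAEs and all adverse events, none of which depends on relatedness. SAP section 14.2 evaluates treatment-emergent events by relationship and separately says that serious events will be summarised; it specifies no related-SAE comparison between arms.

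These points stand and narrow the issue. So does the point that section 18 and section 9.2.20 may describe different judgments, which makes the differing titles an ambiguity and not a proven contradiction. It is also fair to say that nothing in the documents obliges the monitor to make the determination.

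What they do not answer is the central point: section 18 gives an evaluative judgment about the drug to the investigator whom section 22 removes from evaluation, and the conflict plan is silent on it. DSMB review protects patients. It does not settle who fixes the relatedness recorded for each event.

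**Conclusion.** The point holds as a gap in the conflict-of-interest plan, partly mitigated and cheap to close. The PI, who has a declared royalty interest, determines SAE relatedness after consulting the CD, and the available text gives the Independent Medical Monitor no role. The reach is every SAE's recorded relatedness. The size of any bias cannot be computed: no SAE rate is given, and with 33 patients planned per arm the number of related SAEs would be a guess. Nothing in the documents shows that any judgment was in fact biased, and the primary efficacy analysis is not affected.

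The conclusion assumes that no role for the monitor is stated in the pages next to sections 12.4 and 16.2 that were unavailable for this review. It also assumes that relatedness under section 18 takes in relation to study medication, which is the natural but not the only reading.

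**What to change.** - **Section 18:** have relatedness assessed by a blinded treating investigator with no declared interest and confirmed by the Independent Medical Monitor in consultation with the CD. The PI transmits the report but does not set or change relatedness.
- **Sections 9.1.16 and 9.2.20:** name the same assessor, and state whether relatedness to the research and relatedness to study medication are one judgment or two, and which is recorded if assessments differ.
- **Section 22:** add this to the listed safeguards, and reflect it in the monitor's remit in section 16.1.
- **For data already collected:** section 7.6.10 says that data analysis is complete, so an amendment cannot alter past judgments. State in the study report who judged relatedness for each SAE, and have the monitor re-review the recorded SAE relatedness masked to allocation, reporting any changes.

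The cost is the amendment wording and a few more case reviews for the monitor. The roles already exist, and neither the sample size nor any efficacy analysis changes.

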19. ALTERNATIVES TO PARTICIPATION OR ALTERNATIVE THERAPIES

There are currently no therapeutic alternatives with proven therapeutic benefit for PP-MS patients.

20. PRIVACY

All research activities will be conducted in as private a setting as possible.

21. CONFIDENTIALITY

21.1 For medical records

Medical records will be maintained in the NIH Clinical center and released according to NIH regulations and Health Insurance portability and Accountability Act of 1996 (HIPAA) guidelines.

21.2 For research data

Research data will be anonymized and locked in file cabinets if in paper form or in password protected electronic databases maintained on NINDS secure server or on encrypted computers at the NIH. Only study investigators will have access to research data. Anonymized data and results may be shared with Santhera Pharmaceuticals for research purposes and for drug filing with the FDA.

21.3 For stored samples

Coded biological samples will be stored in secure freezers and liquid nitrogen tanks at the NIH. Anonymized samples may be made available for future testing in this or other laboratories following the guidelines of the Office of Human Subjects Research.

22. CONFLICT OF INTEREST/TECHNOLOGY TRANSFER

NIH guidelines on conflict of interest have been distributed to all investigators.

[name] has identified a conflict of interest related to this study. She is one of the co-inventors on an NIH patent related to the use of idebenone as therapeutic agents in humans. This conflict of interest is properly disclosed in the protocol and in the consent form.

To resolve this conflict-of-interest, we have instituted following safeguards:

- [name] will not obtain informed consent and will not serve as the treating or evaluating physician on this protocol.

- [name], a senior NINDS neurologist who is not part of the NIB, will serve as the Independent Medical Monitor under this protocol.
- The independent DSMB will monitor the study.

No other investigators identified any additional conflicts of interest.

A clinical trial agreement (CTA#2009-0004) has been established with Santhera Pharmaceuticals through the NIH/NINDS office of technology transfer (OTT). This agreement specifies that Santhera will provide idebenone without restriction for the clinical study as outlined. All collected raw data will be the sole property of NINDS. Summary data will be made available to Santhera Inc. for regulatory purposes and for stock exchange purposes. Santhera Inc. can use these summary data for other purposes only after consultation with NINDS and only under confidentiality agreement.

23. RESEARCH AND TRAVEL COMPENSATION

Enrolled patients will not be compensated for time and research-related inconveniences.

Enrolled patients will be reimbursed for travel and lodging according to NINDS guidelines (travel form as attachment).

25. ATTCHAMENTS/APPENDICES

25.1 Flow chart

	Pre-treatment Baseline Period (Month -12 - 0)					Idebenone Treatment Period (Month 0-24)			
	Month -12	Month -11	Month -10	Month -6	Month 0 (2 days)	Month 6	Month 12 (2 days)	Month 18	Month 24 (2 days)
Clinical									
Clinical evaluation	√			√	√	√	√	√	√
Inclusion/Exclusion criteria	√				√				
Urinalysis/pregnancy	√		√	√	√	√	√	√	√
Clinical Lab work	√				√	√	√	√	√
Safety Lab work						Every 3 months for the first year and Every 6 months for the second year			
Imaging									
MRI brain 3T (Q 6mo)	√			√	√	√	√	√	√
OCT (Q 12 mo)	√				√		√		√
Immunology									
Research Blood (≤ 60ml)			√		√		√		√
Lymphocytapheresis *	√					√			√
Lumbar puncture	√					√			
Lithium Heparin (5mL) optional			√				√		
Skin biopsy	√								

NB: all studies to be completed within 4 weeks +/- date indicated with exception of baseline lymphocytapheresis, lumbar puncture and skin biopsy, which can be performed anytime during pre-treatment baseline period.

*120 cc of whole blood may be collected in the place of Lymphocytapheresis if there is a contraindication.

25.2 Eligibility checklist

Inclusion criteria

- PP-MS as determined by the 2005 modification of McDonald's diagnostic criteria (*Polman, Reingold et al. 2005*)
- Age between 18-65 years (inclusive)
- EDSS measure of neurological disability from 1 (no disability, clinical signs only) to 7 (ambulatory with bilateral support) (*Kurtzke 1983*)
- Able to provide informed consent
- Willing to participate in all aspects of trial design and follow-up
- Agreeing to commit to the use of reliable method of birth control (i.e. hormonal contraception (birth control pills, injected hormones, vaginal ring), intrauterine device, barrier methods with spermicide (diaphragm with spermicide, condom with spermicide) or surgical sterilization (hysterectomy, tubal ligation, or vasectomy) for the duration of treatment arm of the study
- Not receiving any immunomodulatory/immunosuppressive therapies for a period of at least 3 months before enrollment in the study
- No exposure to idebenone, coenzyme-Q₁₀ or other dietary supplements (such as antioxidants, mitochondrial-function promoting supplements or vitamins in excess of 3 times recommended daily doses) for a period of at least 1 month before enrollment in the study

Exclusion criteria

- Alternative diagnoses that can explain neurological disability and MRI findings
- Clinically significant medical disorders that, in the judgment of the investigators can cause CNS tissue damage or limit its repair, or that would expose the patient to undue risk of harm or prevent the patient from completing the study
- History of hypersensitivity reaction to idebenone or coenzyme Q₁₀
- Pregnant or lactating women. All women of child-bearing potential must have negative pregnancy test prior to the treatment phase of the study.
- Abnormal screening/baseline blood tests exceeding any of the limits defined below:
 - Serum alanine transaminase or aspartate transaminase levels greater than 3 times the upper limit of normal values
 - Total white blood cell count < 3,000/mm³
 - Platelet count < 85,000/mm³
 - Serum creatinine level > 2.0 mg/dl or eGFR (glomerular filtration rate) <30
 - Positive pregnancy test
- Patients who are receiving any immunosuppressive therapies (including cytostatic agents) due to the concern that these drugs may contribute to neurodegeneration or limit CNS repair

23.3 Case Report Forms (CRFs)

Trial data will be captured using the NIH Clinical Research Information System (CRIS) in the structured Neuroimmunology note. Additional data are captured in CRIS that may be useful in verifying the compliance to the study protocol, such as appointment dates, orders, adverse event documentation, etc.

